### **7.3. Lost to Follow-up**

A participant will be considered lost to follow-up if he or she repeatedly fails to return for scheduled visits and is unable to be contacted by the study site.

The following actions must be taken if a participant fails to return to the clinic for a required study visit:

- The site must attempt to contact the participant and reschedule the missed visit as soon as possible and counsel the participant on the importance of maintaining the assigned visit schedule and ascertain whether or not the participant wishes to and/or should continue in the study;
- Before a participant is deemed lost to follow-up, the investigator or designee must make every effort to regain contact with the participant (where possible, 3 telephone calls and, if necessary, a certified letter to the participant's last known mailing address or local equivalent methods). These contact attempts should be documented in the participant's medical record;
- Should the participant continue to be unreachable, he/she will be considered to have withdrawn from the study.

In the event that vital status (whether the participant is alive or dead) is being measured, publicly available information should be used to determine vital status only as appropriately directed in accordance with local law.

Discontinuation of specific sites or of the study as a whole is handled as part of [Appendix 1](#).

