## 4. STUDY DESIGN

### 4.1. Overall Design

This will be a Phase 2, open-label study in healthy participants who received 1 of 6 dose/formulations of GBS6 at the US investigative sites in the C1091001 study. Participants who received placebo in the C1091001 study will not be eligible for study participation.

Healthy men and women will receive a single booster dose of GBS6 (20 µg) formulated with or without AlPO4 based on the formulation received in the primary C1091001 study; ie, participants who received 5 µg, 10 µg, or 20 µg without AlPO4 in C1091001 will receive 20 µg without AlPO4. Participants who received 5 µg, 10 µg, or 20 µg with AlPO4 in C1091001 will receive 20 µg with AlPO4.

Participants will have blood drawn prior to vaccination (Visit 1) and 1 month after vaccination (Visit 2) and will receive a 6-month safety follow-up telephone call (Visit 3). E-diaries will be used to collect prompted local reaction and systemic event data for 14 days after vaccination (Days 1 through 14, where Day 1 is the day of vaccination), and AEs (including MAEs and SAEs) will be collected through Visit 2 and MAEs and SAEs through Visit 3.

An E-DMC will be utilized.

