## **7.2. Participant Discontinuation/Withdrawal From the Study**

A participant may withdraw from the study at any time at his/her own request, or may be withdrawn at any time at the discretion of the investigator for safety, behavioral, compliance, or administrative reasons.

After investigational product administration at Visit 1, participants who request to discontinue further study procedures (eg, blood draw) at an upcoming visit will be asked to remain in the study for protocol-specified safety follow-up procedures. The only exception to this is when a participant specifically withdraws consent for any further contact with him or her.

At the time of discontinuing from the study, please refer to the investigator site file (ISF) and the SoA for assessments to be collected at the time of study discontinuation and follow-up and for any further evaluations that need to be completed. Participants should be questioned regarding their reason for withdrawal. The participant will be permanently discontinued from the study at that time.

If a participant withdraws from the study, he/she may request destruction of any remaining samples, but data already generated from the samples will continue to be available, and may be used to protect the integrity of existing analyses. The investigator must document any such requests in the site study records.

If the participant withdraws from the study and also withdraws consent (see below) for disclosure of future information, no further evaluations should be performed and no additional data should be collected. The sponsor may retain and continue to use any data collected before such withdrawal of consent.

When a participant withdraws from the study because of an SAE, the SAE must be recorded on the CRF and reported on the Clinical Trial (CT) SAE Report.

Lack of completion of all or any of the withdrawal/early termination procedures will not be viewed as protocol deviations so long as the participant's safety was preserved.

Participants who have received the investigational product will not be replaced regardless of the reason for withdrawal.

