#### **8.1.3. Visit 3 – 6-Month Telephone Call (160-200 Days After Visit 1)**

- Ensure that the participant continues to be eligible for the study and meets none of the participant withdrawal criteria as described in [Section 7](#).
- Verify the participant's compliance with the protocol requirements for contraception.
- Record nonstudy vaccinations and concomitant medications as described in [Section 6.5.3](#).
- Record AEs as described in [Section 8.5](#).
- Complete the participant's source documents.
- The investigator or an authorized designee completes the CRF.

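### Protocol 7.3 ties its contact steps to a missed clinic visit and counts an unreachable participant as withdrawn, so the Visit 3 safety call is not stated to remain due after loss at Visit 2, nor clearly covered by those steps when it is missed

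*Protocol*

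**What the plan says.** Protocol 7.3 defines a participant as lost to follow-up if he or she "repeatedly fails to return for scheduled visits and is unable to be contacted by the study site". It then lists required actions under a narrower trigger: "The following actions must be taken if a participant fails to return to the clinic for a required study visit". The actions are to try to reschedule the visit and, "Before a participant is deemed lost to follow-up, the investigator or designee must make every effort to regain contact with the participant", with three telephone calls where possible and a certified letter if needed. The list ends: "Should the participant continue to be unreachable, he/she will be considered to have withdrawn from the study".

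Protocol 7.2, on participants leaving the study, says: "The participant will be permanently discontinued from the study at that time". The same section treats people who decline further procedures differently. After vaccination they "will be asked to remain in the study for protocol-specified safety follow-up procedures", and the only exception is a participant who withdraws consent for any further contact.

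The Schedule of Activities has two contacts after Visit 1: Visit 2, a clinic visit 28-38 days later, and Visit 3, a telephone call 160-200 days later. Protocol 8.1.3 gives no number of attempts for that call and no action if it fails. MAEs and SAEs through 6 months are a primary endpoint (Protocol 9.1.1), actively collected up to and including Visit 3 (8.5.1).

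**The concern.** The 7.3 text suits a study with several clinic visits. Here the trigger is met by missing Visit 2 and, on its wording, not by missing the Visit 3 call. The last bullet then closes participation for someone who could not be reached around Day 28-38, although being out of reach then does not imply being out of reach four or five months later.

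The result is uneven. A vaccinated participant who tells the site that he or she wants no more procedures is asked to stay for safety follow-up. One who has refused nothing and simply could not be reached is counted as withdrawn, and no text keeps the Visit 3 call due.

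At stake is avoidable missing data on a primary safety endpoint, with a known direction of bias.

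**Working it through.** The point rests mainly on wording. The plan has no figure of its own to reproduce: the study is descriptive, and no missed-call or dropout rate is visible (part of Protocol 9.2 is redacted).

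**1. Two paths through the text**

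| Situation | What applies | What is not stated |
|---|---|---|
| Misses Visit 2, still unreachable after the steps | 7.3 last bullet: withdrawn; 7.2: discontinuation is permanent | Whether the Visit 3 call is still attempted |
| Attends Visit 2, cannot be reached for Visit 3 | Section 8 (every effort on required procedures); 8.5.1 (active collection through Visit 3) | Whether the three calls and the letter apply |

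The duties in Section 8 and 8.5.1 reach participants who are still in the study. They do not restore someone already counted as withdrawn.

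**2. Time affected**

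The windows come from the Schedule of Activities.

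- Shortest gap from Visit 2 to Visit 3: 160 − 38 = 122 days, and 122/160 = 76% of follow-up.
- Longest gap: 200 − 28 = 172 days, and 172/200 = 86% of follow-up.

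**3. Direction of the bias**

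SAP 6.1.4 analyses MAEs and SAEs on the safety population. SAP Table 6 requires one dose and at least one later safety assessment for that population, and does not require a completed Visit 3. SAP 2.1.3 uses all collected data and imputes only dates. An uncontacted participant therefore stays in the denominator, and later events count only if the site learns of them some other way. Against the result with the call completed, the numerator can only be equal or lower.

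**4. Illustration of size (assumed rates, not from the documents)**

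Let p be the true 6-month proportion, m the share with no Visit 3 contact, and f the share of 6-month events already known at Visit 2. Take a constant event rate, so f = 30/180, and assume no self-report after Visit 2.

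Expected reported proportion = p × [(1 − m) + m × f]. With p = 10%:

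- m = 5%: 10% × (0.95 + 0.05 × 0.167) = 9.6%, a relative understatement of 4%.
- m = 10%: 10% × (0.90 + 0.10 × 0.167) = 9.2%, or 8%.
- m = 20%: 10% × (0.80 + 0.20 × 0.167) = 8.3%, or 17%.

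For precision, take N = 297, the number of GBS6 recipients who completed C1091001, with both formulations together. At m = 10% about 30 participants would have no call. The count would move from about 30/297 (10.1%, Clopper-Pearson 95% CI 6.9% to 14.1%) to about 27/297 (9.1%, 6.1% to 13.0%).

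For a rare event, take a formulation group of 148 (assumed half of 297) and suppose one SAE is lost. Then 1/148 (0.68%, 95% CI 0.02% to 3.71%) becomes 0/148 (0% to 2.46%). This shows the effect of one lost event; it does not say how likely that loss is.

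These are upper bounds on what the wording costs. The share m includes people no rule would reach, and self-reporting would recover some events.

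**The case against.** A reader might infer that the Visit 3 call is never pursued, or never made. The documents do not support that. Section 8 makes adherence to the schedule mandatory and asks for every effort on required procedures, and 8.5.1 requires active collection through Visit 3. For anyone still in the study the call is required. What is missing is an explicit set of steps when it fails.

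A reader might also infer that the word for repeated failure in the 7.3 definition contradicts the last bullet, because only one return visit exists. Protocol 8.1.4 names Visit 3 among the scheduled visits, and Visit 2 can be rescheduled, so the definition can be met. That wording can stay.

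Three further objections have weight:

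- The permanence sentence in 7.2 follows an instruction to ask participants why they are leaving, so it seems written for people the site is in contact with. Data collection is expressly barred only where consent for disclosure of future information is also withdrawn. Nothing forbids a later call to someone merely unreachable, and the investigator site file, which 7.2 cites, may say more. This shows that the call is permitted; it does not make it due.
- Visit 3 is not the only source of late events. Participants are asked to contact the site about medically attended events and hospitalizations (8.1.1) and significant illness (8.1.4), and related SAEs learned of later must be reported (8.5.1). This limits the loss.
- SAP 6.5.2 tabulates completion of each follow-up visit and withdrawals with reasons, by vaccine group. The loss would be visible, but not recovered.

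**Conclusion.** The point holds as a defect in a stated follow-up rule. Read together, 7.3 and 7.2 leave a vaccinated participant lost at Visit 2 without a stated Visit 3 call, at least 122 days before that window opens (counting from the close of the Visit 2 window), although he or she has not withdrawn consent for contact. They also leave it unclear whether the 7.3 contact steps apply to a missed Visit 3 call.

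The direction is certain given the safety population: missing calls can lower the 6-month MAE and SAE proportions and cannot raise them. The size cannot be known from the documents and is probably small. The illustrative 4% to 17% relative understatement rests wholly on assumed missed-call rates, a constant event rate and no self-report. This is a cheap improvement to a primary safety endpoint and does not threaten the study's conclusions.

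**What to change.** Amend Protocol 7.3 in two places:

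1. Extend the trigger to a participant who misses Visit 2 or cannot be reached for the Visit 3 call, so that the same calls and letter apply to both.
2. State that, for a vaccinated participant who is unreachable at Visit 2, the Visit 3 call is still attempted unless consent for contact was withdrawn, and that final lost-to-follow-up status is assigned only after that attempt.

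The cost is a short protocol amendment and a few extra call attempts by existing site staff. No visit, assessment or analysis is added.

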## **8. STUDY ASSESSMENTS AND PROCEDURES**

The investigator (or an appropriate delegate at the investigator site) must obtain a signed and dated ICD before performing any study-specific procedures.

Study procedures and their timing are summarized in the SoA. Protocol waivers or exemptions are not allowed.

Immediate safety concerns should be discussed with the sponsor immediately upon occurrence or awareness to determine if the participant should continue or discontinue study intervention.

Adherence to the study design requirements, including those specified in the SoA, is essential and required for study conduct.

All screening evaluations must be completed and reviewed to confirm that potential participants meet all eligibility criteria. The investigator will maintain a screening log to record details of all participants screened and to confirm eligibility or record reasons for screening failure, as applicable.

Every effort should be made to ensure that protocol-required tests and procedures are completed as described. However, it is anticipated that from time to time there may be circumstances outside the control of the investigator that may make it unfeasible to perform the test. In these cases, the investigator must take all steps necessary to ensure the safety and well-being of the participant. When a protocol-required test cannot be performed, the investigator will document the reason for the missed test and any corrective and preventive actions that he or she has taken to ensure that required processes are adhered to as soon as possible. The study team must be informed of these incidents in a timely manner.

For samples being collected and shipped, detailed collection, processing, storage, and shipment instructions and contact information will be provided to the investigator site prior to initiation of the study.

## **8.1. Study Procedures**

### **8.1.1. Visit 1 – Vaccination (Day 1)**

- Obtain written informed consent before performing any study-specific procedures.
- Assign a participant number using the IRT system.
- Obtain and record the participant demography (including date of birth, sex, race, and ethnicity). The full date of birth will be collected to critically evaluate the immune response and safety profile by age.
- Obtain and record any medical history of clinical significance.
- Perform physical examination evaluating any clinically significant abnormalities within the following body systems: general appearance; skin; head, eyes, ears, nose, and throat; heart; lungs; abdomen; musculoskeletal; extremities; neurological; and lymph nodes. Abnormal results must be recorded on source documents and the Physical Examination page of the CRF.
- Ensure and document that all of the inclusion criteria, none of the exclusion criteria, and none of the temporary delay criteria are met.
- Prior to vaccination, measure vital signs, including weight, height, sitting blood pressure and pulse rate, respiratory rate, and temperature (oral).
- Prior to vaccination, perform a urine pregnancy test for WOCBP and ensure the result is negative.

- Prior to vaccination, collect a blood sample of approximately 50 mL for immunogenicity assessments.
- Verify the participant's understanding of and compliance with the protocol requirements for contraception. Instruct the participant to use appropriate contraceptives until 3 months after administration of investigational product and document the conversation and the participant's affirmation in the participant's source document.
- Obtain participant investigational product container number using the IRT system and prepare the investigational product. Please refer to the IP manual for further instruction on this process.
- Administer a single 0.5-mL injection of investigational product into the deltoid muscle CCI
- Site staff must observe the participant for at least 30 minutes after investigational product administration for any acute reactions. Record any acute reactions in the participant's source documents and on the AE page of the CRF, and on an SAE form as applicable.
- Issue the participant a measuring device to measure local reactions and a digital thermometer to measure daily temperatures, and provide instructions on their use.
- Issue the participant an e-diary and provide instructions on its completion. Ask the participant to complete the e-diary from Day 1 to Day 14, with Day 1 being the day of vaccination.
- Ask the participant to contact the site staff or investigator immediately if he or she is prompted by the e-diary from Day 1 to Day 14 following vaccination to determine if an unscheduled visit is required (eg, redness or swelling at the injection site measuring >20 measuring device units [ $>10$  cm]). Remind participants that study staff may contact them to obtain additional information on Grade 3 (or above) events entered into the e-diary.
- Ask the participant to contact the site staff or investigator if a medically attended event (eg, emergency room) or hospitalization occurs.
- Provide the participant with a contact card (see [Section 10.1.10](#) for description of the contact card).
- Record nonstudy vaccinations and medications as described in [Section 6.5.3](#).
- Record AEs as described in [Section 8.5](#).
- Complete the participant's source documents.
- The investigator or an authorized designee completes the CRF and a site staff member updates the investigational product accountability records.

- The investigator or appropriately qualified designee reviews the e-diary data online following vaccination to evaluate participant compliance and as part of the ongoing safety review.

#### **8.1.2. Visit 2 – 1-Month Follow-up Visit (28-38 Days After Visit 1)**

- Ensure that the participant continues to be eligible for the study, meets none of the participant withdrawal criteria as described in [Section 7](#), and meets none of the blood draw temporary delay criteria as described in [Section 5.2.1.2](#).
- Verify the participant's understanding of and compliance with the protocol requirements for contraception.
- Collect a blood sample of approximately 50 mL for immunogenicity assessments. Alternatively, for participants who have consented to participate, collect approximately 150 mL of blood.
- Review the participant's e-diary data and collect the e-diary. Collect stop dates of any e-diary events ongoing on the last day that the e-diary was completed and record stop dates in the CRF.
- Record nonstudy vaccinations and concomitant medications as described in [Section 6.5.3](#).
- Record AEs as described in [Section 8.5](#).
- Complete the participant's source documents.
- The investigator or an authorized designee completes the CRF.

#### **8.1.3. Visit 3 – 6-Month Telephone Call (160-200 Days After Visit 1)**

- Ensure that the participant continues to be eligible for the study and meets none of the participant withdrawal criteria as described in [Section 7](#).
- Verify the participant's compliance with the protocol requirements for contraception.
- Record nonstudy vaccinations and concomitant medications as described in [Section 6.5.3](#).
- Record AEs as described in [Section 8.5](#).
- Complete the participant's source documents.
- The investigator or an authorized designee completes the CRF.

#### **8.1.4. Unscheduled Visits**

If the participant reports redness or swelling at the injection site measuring >20 measuring device units (>10 cm), fever  $\geq 102.1^{\circ}\text{F}$  ( $\geq 39.0^{\circ}\text{C}$ ), or severe injection site pain,

nausea/vomiting, diarrhea, headache, fatigue, muscle pain, or joint pain, a telephone contact must occur as soon as possible between the participant and the investigator or a medically qualified member of the study site staff to assess if an unscheduled visit is required. A site visit must be scheduled as soon as possible to assess the extent of the reaction unless:

- The participant is unable to attend the unscheduled visit, or
- The reaction is no longer present at the time of the telephone contact, or
- The participant recorded an incorrect value in the e-diary (confirmation of an e-diary data entry error), or
- The investigator determined it was not needed.

This telephone contact will be recorded in the CRF and in the participant's source documentation.

If the participant is unable to attend the unscheduled visit, any ongoing reactions must be assessed at the next scheduled visit (Visit 2 and/or Visit 3).

The reactions should be assessed by the investigator or a medically qualified member of the study staff such as a study physician or a study nurse, as applicable to the investigator's local practice, who will:

- Measure oral temperature.
- Measure minimum and maximum diameters of redness (if present).
- Measure minimum and maximum diameters of swelling (if present).
- Assess any injection site pain that is present in accordance with the grading scale provided in [Section 8.4.2](#).
- Assess for lymphadenopathy associated with any present local reaction.
- Assess any systemic events (nausea/vomiting, diarrhea, headache, fatigue, muscle pain, or joint pain) that are present in accordance with the grading scale provided in [Section 8.4.2](#).

The investigator or an authorized designee will complete the unscheduled visit page of the CRF.

Participants will also be instructed to contact site staff if they experience any possible Grade 4 prompted systemic event (ie, emergency room visit or hospitalization for nausea/vomiting, diarrhea, headache, fatigue, muscle pain, joint pain) within 14 days after vaccination. Study staff may contact the participant to obtain additional information on Grade 3 events entered into the e-diary. Lastly, participants will be instructed to contact the

site to report any significant illness, medical event, or hospitalization that occurs during the study period. The site should determine if an unscheduled visit to further evaluate the event is warranted in all such cases.

## **8.2. Efficacy Assessments**

Not applicable.

## **8.3. Immunogenicity Assessments**

Blood samples (approximately 50 mL/visit) for immunogenicity assessments will be collected from all participants prior to vaccination (Day 1) and at 1 month after vaccination; or approximately 150 mL (an additional optional 100 mL) for those participants who consent to a larger blood draw at Visit 2. Sample collection, processing, storage, and shipping information can be found in the **CCI** [REDACTED]. Sera will be used for immunogenicity assessments, assay development, and routine assay maintenance.

OPA results for the 6 serotypes (Ia, Ib, II, III, IV, V) will be determined in all participants for each blood sample at Day 1 and at 1 month after vaccination. Results will be reported as OPA titers.

Concentrations of anticapsular IgG for the 6 serotypes (Ia, Ib, II, III, IV, V) will be determined in all participants for each blood sample at Day 1 and at 1 month after vaccination and reported as IgG concentrations.

Immunogenicity assays will be performed at Pfizer Vaccine Research & Development Laboratory located at [name] and/or at a facility designated by Pfizer.

